### Appendix 3. Oxygen requirements as a proxy for disease severity (listed from lowest to highest disease severity)

- Room air
  - No documentation of the other categories listed below
- Basic oxygenation
  - Includes: Simple face mask, nasal cannula, CPAP/Bubble CPAP, T-piece, blow by, nasal prongs, open oxygen mask, tracheostomy collar, venturi mask system (if FiO2 % is < 45%), face tent (if FiO2 % is < 45%; up to 6L), nasal cannula with reservoir (i.e. oximizer; if FiO2 % is < 45%; up to 6L)
- Advanced oxygenation
  - Includes: High flow nasal cannula (HFNC), BiPAP/NPPV/NIV, Vapotherm, blender system, high flow mask, manual resuscitator, non-rebreather mask (NRB), Oxyhood, partial rebreather mask, venturi mask system (if FiO2 % is ≥ 45%), face tent (if FiO2 % is ≥ 45%; ≥ 7L), nasal cannula with reservoir (i.e. oximizer; if FiO2 % is ≥ 45%; ≥ 7L)
- Invasive ventilation
  - Transtracheal catheter, Invasive mechanical ventilation vent mode
    - CPT code 94002 (mechanical ventilation for initial day), 94003 (subsequent day), 94004 (per day)
- ECMO

NOTE: In cases where clinical flow sheets do not contain sufficient information to classify the level of oxygen support, categorization will be based on clinician review of the electronic health record

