The propensity score is defined as the probability of a patient receiving convalescent plasma conditioned on their observed baseline covariates. Baseline is defined as the period prior to and including the index date. Baseline covariates for the propensity score modeling is listed below and further defined in Appendix 2. To account for confounding by baseline covariates described below, a logistic regression will be fitted to estimate the probability of receiving convalescent plasma. In the event of low frequency of certain covariates, that may cause model convergence problem, such covariates will be removed from the propensity score model. Covariates that are strongly related to convalescent plasma transfusion but only weakly related to the primary outcome will not be included in the propensity model to preserve precision of the estimates. Exposed and unexposed patients will be matched according to propensity score with nearest neighbor caliper matching algorithm without replacement with a match ratio up to 1:4 based on the power calculation (Section V. Sample Size). Propensity density plots pre- and post-matching will be evaluated for overlapping areas.

- Age (continuous)
- Race and ethnicity
- Hospital site
- Comorbidities
- Concomitant medications
- Oxygen requirements as a proxy for disease severity (Appendix 3) 4-12 hours prior to the index date

- Laboratory results: creatinine, D-dimer, troponin, absolute lymphocyte count, ferritin, C-reactive protein
- Vital signs: Respiratory rate (min), Heart rate (min), Systolic BP (mmHg), Temperature (°C)

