### Secondary Analyses

- 1) If sample size allows, stratify analyses by mechanical ventilator use prior to or at the index date
- 2) If sample size allows, subgroup analyses comparing patients who received convalescent plasma and remdesivir, with those who only received remdesivir.
- 3) If sample size allows, stratify analyses by time interval from hospital admission to the index date (<72 hours vs. ≥72 hours).
- 4) If sample size allows, stratify analyses by disease severity measured by oxygenation.

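### Appendix 3 applies its 45% FiO2 split to three devices but not to CPAP, and has no rule for CPAP that is also NPPV/NIV, so the severity covariate can understate severity

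*Protocol*

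**What the plan says.** Protocol Appendix 3 defines five levels, "listed from lowest to highest disease severity": room air, Basic, Advanced, invasive ventilation, ECMO.

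- **Basic:** "Includes: Simple face mask, nasal cannula, CPAP/Bubble CPAP, T-piece", and further devices. CPAP carries no FiO2 or flow condition.
- **Advanced:** "Includes: High flow nasal cannula (HFNC), BiPAP/NPPV/NIV, Vapotherm, blender system", and further devices. NPPV/NIV carries no FiO2 condition either.
- **Split devices:** venturi mask, face tent and reservoir cannula are Basic below FiO2 45% and Advanced at 45% or more. The last two also have a flow limit.
- **Fallback:** a note provides for clinician review "In cases where clinical flow sheets do not contain sufficient information to classify the level of oxygen support".

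The scale is used in two places. Cohort Sampling, step 4, lists it as a propensity score covariate: "Oxygen requirements as a proxy for disease severity (Appendix 3) 4-12 hours prior to the index date". Secondary Analyses, item 4, plans, if sample size allows, to "stratify analyses by disease severity measured by oxygenation". The Covariates section takes the worst oxygenation measure in the window.

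**The concern.** Two features of Appendix 3 sit badly with a scale that claims to be ordered by severity.

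1. **The FiO2 split is uneven.** A venturi mask at FiO2 45% is Advanced. CPAP at, say, 80% is Basic, on a level with a nasal cannula.
2. **Categories can overlap.** CPAP delivered by mask is itself non-invasive positive-pressure support. The Abbreviations list defines none of CPAP, NPPV or NIV, and Appendix 3 has no tie-break. The same support can be coded Basic or Advanced according to the label in the flow sheet.

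The Limitations section names severity differences at index as a route to bias in either direction. This scale is the main tool against them as far as oxygen requirement goes. Cohort Sampling, step 4, and Appendix 2 list respiratory rate, other vital signs and laboratory values, but no oxygen saturation, PaO2 or FiO2.

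**Working it through.** The plan states no figure on this point, so there is none to reproduce. The check is of the text, followed by an illustration of size.

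**Step 1: does anything in the protocol correct the coding?**

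| Safeguard | Where | Effect on a plainly charted high-FiO2 CPAP record |
|---|---|---|
| Clinician review | Appendix 3, note | Not triggered: the record is sufficient to classify |
| Comparison with manual chart review, 95% match | Data Sources | Passes: it tests extraction, not the category definition |
| Worst measure in the window | Covariates | Helps only if a higher level was also recorded in the window |
| Standardized difference above 0.1 leads to Cox adjustment | Comparative Analyses | Not triggered: it compares the coded level |

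Whether the scale enters the model as ordered or as categories, everyone in Basic receives the same oxygenation term.

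**Step 2: what the balance check would miss.** Let p1 and p0 be the shares of high-FiO2 CPAP among exposed and unexposed Basic patients. Both are assumptions. For p1 = 10% and p0 = 5%, the standardized difference within Basic is

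(0.10 − 0.05) / √[(0.10×0.90 + 0.05×0.95)/2] = 0.05 / 0.262 = 0.19.

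If Basic made up half of each group (also an assumption), the whole-cohort shares would be 5% and 2.5%, and the value 0.025 / √[(0.05×0.95 + 0.025×0.975)/2] = 0.025 / 0.190 = 0.13. Both exceed the plan's 0.1 threshold. Neither can appear, because high-FiO2 CPAP is not separated within Basic.

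**Step 3: bias factor within Basic, with no effect of plasma.** Let R be the mortality ratio of high-FiO2 CPAP patients to other Basic patients (an assumption). Then

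B = [1 + p1(R − 1)] / [1 + p0(R − 1)].

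| R | p1 10%, p0 5% | p1 5%, p0 10% | p1 5%, p0 2% | p1 2%, p0 5% | 5% in both |
|---|---|---|---|---|---|
| 1.5 | 1.050/1.025 = 1.02 | 0.98 | 1.025/1.010 = 1.01 | 0.99 | 1.00 |
| 2 | 1.10/1.05 = 1.05 | 0.95 | 1.05/1.02 = 1.03 | 0.97 | 1.00 |
| 3 | 1.20/1.10 = 1.09 | 0.92 | 1.10/1.04 = 1.06 | 0.95 | 1.00 |

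A wider gap gives more: 10% against 2% with R = 3 gives 1.20/1.04 = 1.15, or 0.87 reversed.

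**Step 4: scale.** Table 1 lists detectable relative risks from 0.61 to 0.81. Within Basic, a true ratio of 0.75 would read 0.75 × 1.09 = 0.82 or 0.75 × 0.92 = 0.69 at the ends of the 10%/5% range. The factor applies to a risk ratio within one level, before any adjustment by other covariates. In the whole-cohort hazard ratio it is diluted by patients at other levels.

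**The case against.** The strongest reply is that this is a debatable coding choice with no demonstrated effect. Much of that stands.

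- **Matching.** A reader might infer that such a patient is matched as mildly ill. The protocol does not support that. Oxygen level is not a risk-set matching variable. It is one term in a propensity score that also holds respiratory rate, other vital signs, six laboratory values, comedications, comorbidities and site. Basic ranks above room air, and the protocol never calls it mild.
- **Worst-measure rule.** A CPAP patient who also had high-flow nasal cannula, NIV, a non-rebreather mask or intubation in the window is coded Advanced or higher. Only those whose worst recorded support is CPAP are affected.
- **Contradiction.** A reader might call this a breach of a general FiO2 rule. Appendix 3 has no such rule: it classifies mainly by device and splits three of them. T-piece, tracheostomy collar and simple face mask are not split either. The split is uneven, which is less than a contradiction.
- **Direction.** A reader might infer bias against plasma. That needs more high-FiO2 CPAP among the exposed, which the protocol does not show.
- **Already acknowledged.** Limitations mentions covariate misclassification and lists bias analyses and E-values, if feasible. Appendix 4 will define data elements. Secondary analysis 4 is conditional on sample size.

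The reply does not remove the defect. No other covariate measures oxygen requirement, and the Appendix 4 table does not change a category that Appendix 3 fixes. A conditional general bias analysis does not replace a coding rule that can be settled now. In the oxygenation strata the affected patients sit directly in the wrong group, if those analyses are run.

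**Conclusion.** The point holds as a defect in how the severity covariate is coded, worth correcting before outcomes are compared. High-FiO2 CPAP, when it is the worst support in the window, is placed at the second-lowest of five levels, and CPAP that is also NPPV/NIV has no assigned place. Severity can therefore be understated in the propensity score's only oxygenation covariate and in the strata of secondary analysis 4, out of sight of the balance check.

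Bias in the primary hazard ratio is not shown. It requires the share of high-FiO2 CPAP to differ between the groups after matching, and the protocol gives neither CPAP frequency nor mortality by device. On assumed shares of 10% and 5% and a mortality ratio up to 3, the factor within Basic is about 0.92 to 1.09 depending on direction, and 1.00 if the shares are equal. The effect on the whole-cohort estimate would be smaller.

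**What to change.** This concerns coding for the analysis only, not patient care. In Appendix 3:

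1. Code CPAP by the cut-off already used for the split devices: Basic below FiO2 45%, Advanced at 45% or more.
2. Code CPAP that is delivered or charted as NPPV/NIV as Advanced. The cut-off alone would not settle this overlap.
3. Where FiO2 is not recorded for CPAP, use the existing clinician-review note.

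Use the recoded scale in the propensity score, the balance table and secondary analysis 4. Report the number of CPAP patients by exposure group, so that readers can see whether the issue is material. As a sensitivity analysis, repeat the primary analysis and the oxygenation-stratified analysis with all CPAP coded Advanced. This also covers low-FiO2 CPAP, which would otherwise stay Basic while low-FiO2 NIV is Advanced. No change is asked for simple face mask.

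The cost is one edit to Appendix 3, a change to the flow-sheet mapping and one more sensitivity run. FiO2 is already needed for three other devices, but it may not be charted for every CPAP record, so some chart review will be added.

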**Appendix 4. The location and definition of the data elements**

This table will be created as part of documentation of programming and validation.

Domain	Data Elements	Definition	Time Points	Source system location

Acute myocardial infarction	I21.xx	Acute myocardial infarction
	I22.x	Subsequent ST elevation (STEMI) and non-ST elevation (NSTEMI) myocardial infarction
Stroke	I63.xxx	Cerebral infarction

Safety outcomes	ICD-10-CM	ICD-10-CM Description
	I65.xx	Occlusion and stenosis of precerebral arteries, not resulting in cerebral infarction
	I66.xx	Occlusion and stenosis of cerebral arteries, not resulting in cerebral infarction
	I67.6	Nonpyogenic thrombosis of intracranial venous system
	G45.x;	Transient cerebral ischemic attacks and related syndromes
	G46.x	Vascular syndromes of brain in cerebrovascular diseases
	I61.x;	Nontraumatic intracerebral hemorrhage
	I62.0x;	Nontraumatic subdural hemorrhage
	I62.9	Nontraumatic intracranial hemorrhage, unspecified
Arterial embolism and thrombosis	I74.xx	Arterial embolism and thrombosis
